9.2.5. Analytical Procedures

Serum samples will be analyzed to determine concentrations of daratumumab or generation of antibodies to daratumumab using validated immunoassay methods by or under the supervision of the sponsor's bioanalytical facility.

For the immunogenicity assessments, serum samples will be screened for antibodies binding to daratumumab and serum titer will also be determined from confirmed positive samples. Other immunogenicity analyses (eg, assessment of neutralizing capabilities) may be performed to further characterize the immune responses that are generated.

For Phase 2, all samples collected and received up to the time of the primary study endpoint analysis (first bioanalysis) will be analyzed for serum daratumumab concentration as indicated by the Time and Events Schedule. All data from this first analysis will be considered final and these samples will not be reanalyzed at the end of the study. The final bioanalysis will include all immunogenicity (from Phases 1 and 2) and any remaining pharmacokinetic samples that become available after the primary endpoint analysis. Adjustments to bioanalysis timing may be made if it is later determined that the timing for data needed to facilitate crucial decision-making differs from these 2 planned efforts. However, data from each round of bioanalysis will be considered final and samples will not be reanalyzed in any subsequent efforts.

9.2.6. Pharmacokinetic Parameters

The pharmacokinetic parameters are defined as:

CL Total systemic clearance of drug after IV administration

C_{max} Maximum observed concentration C_{min} Minimum observed concentration

V Volume of distribution

Pharmacokinetic samples to determine serum concentration of daratumumab will be obtained from all subjects. The pharmacokinetic parameters include but may not be limited to the following:

- Minimum observed concentration (Cmin)
- Maximum observed concentration (Cmax)

If sufficient data are available, then other pharmacokinetic parameters may be calculated, including but not limited to total systemic clearance of drug after IV administration (CL) and volume of distribution (V).

9.2.6.1. Immunogenicity Assessments

Serum from venous blood samples will be assessed for the generation of antibodies to daratumumab (immunogenicity) according to the Time and Events Schedule. Daratumumab concentration is also evaluated at all immunogenicity time points (Phases 1 and 2) to ensure

appropriate interpretation of immunogenicity data. When both serum concentration and immunogenicity analyses are specified, they are performed on aliquots from the same blood draw and no additional sampling is required. Procedures for sample collection, preparation, identification, storage, and shipment will be provided in the Laboratory Manual or equivalent document.

A blood sample should be drawn, if possible, for determination of antibodies to daratumumab any time an infusion reaction is observed or reported during the study. Daratumumab serum concentration will also be determined from the same infusion reaction sample for the purpose of interpreting immunogenicity data. These samples will be stored and evaluated if deemed necessary. If the infusion reaction results in treatment discontinuation, then subjects should undergo all scheduled safety and efficacy evaluations. Samples collected for the analysis of daratumumab immunogenicity/serum concentration may additionally be used to evaluate safety or efficacy aspects that address concerns arising during or after the study period or for the evaluation of relevant biomarkers by the sponsor or sponsor's designee.

9.2.6.2. Biomarker Assessments

9.2.6.2.1. Phase 1 Biomarker Analyses

9.2.6.2.1.1. Levels of Soluble CD38

A blood sample will be drawn for analysis of soluble CD38. The samples will be stored at the central laboratory until a validated assay is available.

9.2.6.2.1.2. Complement

A blood sample will be drawn for analysis of complement (CH50) at visits as indicated in Table 1. This blood sample must be drawn 2 hours after the end of infusions. Analysis of complement will be done in batches of several samples.

9.2.6.2.1.3. Levels of Circulating NK Cells, B, and T Cells (Flow Cytometry)

A blood sample will be drawn for analysis of the following immune cell populations:

CD45+CD38+	CD45+CD19+	CD45+CD3+	CD45+CD3+CD4+
CD45-CD138+	CD45+CD3+CD8+	CD45+CD138+	CD3-CD56+
CD3-CD16+CD56+ CD45+CD138+CD38+			

Additional flow cytometry subgroups may be added for exploratory purposes.

9.2.6.2.2. Phase 2 Biomarker Analyses

Biomarker analyses are dependent upon the availability of appropriate biomarker assays and may be deferred or not performed if during or at the end of the study it becomes clear that the analysis will have no scientific value, or if there are not enough samples or not enough responders to allow for adequate biomarker evaluation. In the event the study is terminated early or shows poor clinical efficacy, completion of biomarker assessments is based on justification and intended

utility of the data. Samples for biomarker evaluations will be collected for all subjects as specified in Table 2.

Biomarker analyses will be focused on further understanding the MOA (ADCC/CDC/ADCP) of daratumumab in combination with lenalidomide and dexamethasone, evaluating predictive markers of response to daratumumab, and determining whether daratumumab can reduce minimal residual disease in patients who achieve a complete response. Whole blood samples will be utilized for immunophenotyping, which includes analysis of NK, T, and B cells. NK cells are known to express CD38 and early clinical data indicates they are rapidly depleted upon daratumumab dosing. Additional immune cell populations that may be studied include macrophages, dendritic cells, myeloid derived suppressor cells, or other flow cytometry subgroups that may be added for exploratory purposes. ADCC and CDC may be evaluated to determine whether lenalidomide and dexamethasone help preserve effective ADCC despite NK cell depletion. T-cell receptor sequences may be evaluated from whole blood PBMC DNA to determine if specific clonal CD8+ T-cell expansion occurs with daratumumab treatment and if this is associated with clinical response.

In addition to whole blood collections, bone marrow aspirates will be collected for biomarker evaluations including multiple myeloma cell phenotyping, evaluation of CD38 and complement inhibitory protein (CIP) expression (CD46/CD55/CD59). Soluble CD38 expression levels may be evaluated in plasma to determine if sCD38 levels influence daratumumab serum levels and are associated with daratumumab response. Serum samples may also be analyzed for complement proteins or for complement dependent cytotoxicity (CDC), which is one mechanism of action for daratumumab. Exploratory proteomics may be utilized to evaluate cytokines, complement proteins, complement associated proteins, soluble CD38, soluble CD46/CD55/CD59, or other proteins associated with daratumumab response and/or resistance.

9.2.6.2.3. Phase 2 Pharmacogenomics

A pharmacogenomic blood sample will be collected to allow for pharmacogenomic research, as necessary (where local regulations permit). Subject participation in the pharmacogenomic research is optional.

Several pharmacogenomics assessments may be performed for those subjects who consent to genomic analyses. A blood sample will be collected and processed to extract DNA, which may be evaluated for single nucleotide variation in genes associated with immune-mediated tumor cell lysis and potentially daratumumab response/resistance. The following single nucleotide polymorphisms (SNP) may be measured: FcgR2A-R131H, FcgR2A-Q62R, FcgR2A-Q62X, FcgR3A-V158F, FcgR3A-V212F, FcgR2B-I232T, and C1QA-A276G. In addition, assessment of copy number variation in FcgR2C, FcgR3A, and FcgR3B may be performed on this sample. Additional polymorphisms, single nucleotide polymorphisms, or copy number variations may be added for exploratory purposes. These genotypes may be evaluated for potential predictive biomarkers as well as for association with daratumumab response and with levels of functional ADCC and CDC before daratumumab treatment. Pharmacogenomic assessments may also

include evaluation of T-cell response through T-cell receptor sequencing from PBMCs isolated from whole blood.

9.3. Endpoints

The primary endpoint for this study will be the incidence of AEs.

The secondary endpoints are:

- The rate of response according to the International Uniform Response Criteria (Rajkumar 2011) ²¹
- PK variables (AUC, C_{max} , minimum or trough concentration in serum [C_{min}], time to C_{max} [T_{max}], apparent clearance [CL], volume of distribution [V], and elimination half-life [$t_{1/2}$])
- Time to progression
- Duration of response
- Progression-free survival (PFS)

10. SUBJECT COMPLETION/WITHDRAWAL

Completion

Subjects will be considered as having completed the study if he/she has consented to Amendment 8

10.1. Discontinuation of Study Treatment

A subject's study treatment should be discontinued if:

- The investigator believes that for safety reasons (eg, adverse event) it is in the best interest of the subject to discontinue study treatment
- The subject becomes pregnant
- The subject has documented PD
- The subject withdraws consent for further treatment
- Treatment is delayed for more than 3 weeks and no approval to continue is given by the sponsor.

If a subject discontinues study treatment or is transferred to commercial supplies, as per Amendment 8, follow-up for the occurrence of SPM will continue for up to 3 years after the last dose of lenalidomide.

10.2. Withdrawal

A subject will be withdrawn from treatment for any of the following reasons:

- DLT
- DVT and/or PE

- Tumor lysis syndrome
- Grade 3 skin rash
- Pregnancy
- Subject choice
- Investigator decision
- Disease progression
- Initiation of new treatment against multiple myeloma
- Lost to follow-up
- Intercurrent illness that precludes further participation or requires a prohibited concomitant treatment
- Treatment is delayed for more than 3 weeks and no approval to continue is given by the sponsor
- Other

If a subject discontinues study treatment or is transferred to commercial supplies, as per Amendment 8, follow-up for the occurrence of SPMs will continue for up to 3 years after the last dose of lenalidomide.

The investigator, in consultation with the subject, will decide the future course of treatment for multiple myeloma.

If a subject is lost to follow-up, every reasonable effort must be made by the study site personnel to contact the subject and determine the reason for discontinuation/withdrawal. The measures taken to follow up must be documented.

A subject who withdraws from treatment will have the following options regarding the optional research samples:

- The collected samples will be retained and used in accordance with the subject's original separate informed consent for optional research samples.
- The subject may withdraw consent for optional research samples, in which case the samples will be destroyed and no further testing will take place. To initiate the sample destruction process, the investigator must notify the sponsor study site contact of withdrawal of consent for the optional research samples and to request sample destruction. The sponsor study site contact will, in turn, contact the biomarker representative to execute sample destruction. If requested, the investigator will receive written confirmation from the sponsor that the samples have been destroyed.

Withdrawal From the Optional Research Samples While Remaining in the Main Study

The subject may withdraw consent for optional research samples while remaining in the study. In such a case, the optional research sample[s] will be destroyed. The sample destruction process will proceed as described above.

Withdrawal From the Use of Samples in Future Research

The subject may withdraw consent for use of samples for research (refer to Section 16.2.5, Long-Term Retention of Samples for Additional Future Research). In such a case, samples will be destroyed after they are no longer needed for the clinical study. Details of the sample retention for research are presented in the main ICF [and in the separate ICF for optional research samples].

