Throughout the protocol	Minor grammatical, formatting, or spelling changes were made.

Amendment 2 (23 February 2012)

This amendment is considered to be nonsubstantial based on the criteria set forth in Article 10(a) of Directive 2001/20/EC of the European Parliament and the Council of the European Union, in that it does not significantly impact the safety or physical/mental integrity of subjects, nor the scientific value of the study.

The overall reason for the amendment: This amendment includes a correction to the reasons for withdrawal of subjects from treatment.

Applicable Section(s)	Description of Change(s)
Rationale: Withdrawal	
Section 10.2	During review of the protocol, the Medicines and Healthcare products Regulatory Agency noted that subjects must be withdrawn from treatment due to pregnancy. Further review of the protocol by the sponsor indicated that Section 10.2 stated that subjects may be withdrawn from treatment for the reasons listed (including pregnancy). This amendment corrects that statement to clarify that subjects will be withdrawn from treatment for any of the reasons listed.

Amendment 1 (03 February 2012)

This amendment is considered to be substantial based on the criteria set forth in Article 10(a) of Directive 2001/20/EC of the European Parliament and the Council of the European Union.

The overall reason for the amendment: This amendment includes clarification of an exclusion criterion, and changes to an inclusion criterion, vital sign assessments, the laboratory analyzing electrocardiograms, bone marrow assessments, the definition of dose-limiting toxicities, and informed consent. Details of and reasons for the changes are presented below.

Applicable Section(s)	Description of Change(s)								
Rationale: Inclusion Criterion #2									
Synopsis and Section 4.2	Key opinion leaders have advised Genmab to include only patients with measurable M-component in blood or urine. Patients who have involved free light chain levels but no measurable M-component are difficult to evaluate. I is, therefore, the opinion of Genmab and key opinion leaders that including this population could distort evaluation of both safety and efficacy assessments in this small trial and result in ambiguous conclusions. To avoid any unclear and misleading results of GEN503, Genmab has opted to exclud these patients from the trial.								
Rationale: Exclusion Criterion #16									

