continue the other components until progression or commencing a new regimen for the treatment of multiple myeloma. However, subjects will still receive dexamethasone as premedication to daratumumab.

In Phase 1, to minimize the risk of cytokine release syndrome, the first infusion of the first cycle will be preceded by a predose infusion the day before the scheduled full-dose infusion. The predose infusion will be 10% of the full dose, but will never be more than 10 mg in total dose. Further measures to prevent cytokine release syndrome will include premedication with antihistamines, acetaminophen, and dexamethasone before each daratumumab infusion (both predose and full dose).

Lenalidomide will be administered at a dose of 25 mg orally (PO) on Days 1 through 21 of each 28-day cycle, and dexamethasone will be administered at a total dose of 40 mg weekly. Further details on the administration of dexamethasone are provided in the Test Product, Dose and Mode of Administration section of this synopsis.

During Phase 1, decisions to escalate the dose of daratumumab for the next cohort will be based on the safety data obtained from the 3 (+ 3) subjects in the previous cohort during their first treatment cycle (28 days). The Independent Data Monitoring Committee (IDMC) will evaluate all safety data (including serious adverse events [SAEs], adverse events [AEs], and laboratory data) after each cohort completes Cycle 1. The third subject in the cohort must have received all 4 full doses of daratumumab, and data from an observation period of 6 days after the last infusion must be available for the IDMC to review. Based on the results presented in these safety profiles, the IDMC will recommend to the sponsor if it appears safe to escalate the dose. The recommendation will be discussed and confirmed by the sponsor, who will ultimately decide if dose escalation will occur. Subjects who discontinue the study during the first cycle for reasons other than a DLT will be replaced.

The RP2D dose selected is 16 mg/kg based upon marked M-protein reduction with an acceptable safety profile in doses up to 16 mg/kg, the highest dose of Phase 1. In addition, the following data from Phase 1 of this combination study and data at 16 mg/kg in ongoing monotherapy studies is supportive of the RP2D dose.

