6.2.1.5. Other Grade 3 or 4 Adverse Events

For other Grade 3 or 4 toxicities judged by the investigator to be related to lenalidomide alone, treatment with lenalidomide should be interrupted and restarted at the next lower dose level once the toxicity has resolved to Grade 2 or less. Treatment with daratumumab and dexamethasone may continue.

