6.4. Delaying or Skipping Treatment

After completion of each cycle, initiation of a new cycle should be delayed for at least 1 week if the subject experiences toxicity. A subject whose cycle is delayed should be evaluated weekly for resolution or recovery of the toxicity, and a decision regarding further delay or initiation of

Key: CrCl = creatinine clearance.

Estimated by CrCl as calculated by the Cockcroft-Gault, Diet in Renal Disease (MDRD), or Chronic Kidney Disease Epidemiology Collaboration (CKD-EPI) formulas formula (Attachment 7).

the next cycle should be made. However, the start of a new cycle after more than a 3-week delay (with all study therapy withheld) may occur only if there is clear clinical benefit and only after approval by the sponsor.

Refer to Section 6.6.1 for details on management of infusion-related reactions. **ONLY if any of the following criteria below are met, and the event cannot be ascribed to lenalidomide, the daratumumab infusion must be held to allow for recovery from toxicity**. The following parameters must be met on the first day of a new cycle (after Cycle 1):

- Platelet count $\geq 50 \times 10^9/L$
- Febrile neutropenia of any grade
- Neutropenia with infection, of any grade
- Hemoglobin $\geq 8.0 \text{ g/dL}$ ($\geq 4.96 \text{ mmol/L}$) (prior red blood cell transfusion or recombinant human erythropoietin use is allowed)
- ANC $\ge 0.75 \times 10^9 / L$
- Nonhematologic toxicity of Grade 3 or higher must have recovered to baseline or Grade 1 or less unless otherwise specified

A subject whose cycle is delayed should be evaluated at least weekly for resolution of the toxicity. For severe hematologic toxicity (Grade 3 or higher), a complete blood count may be repeated more frequently as necessary until the requirements for reinitiating treatment are met.

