6.5. Dose-limiting Toxicities

Overall toxicity occurring during the first treatment cycle of each cohort will be used to assess DLTs for the purposes of dose escalation and subsequent dose assignment. Dose-limiting toxicities must be reported to the sponsor within 24 hours.

Dose-limiting toxicities are defined as any of the following events that occur during the first treatment cycle (28 days):

- Nonhematologic toxicity considered to be a serious adverse event (SAE) of grade 3 or higher and related to daratumumab with the exception of:
 - Any nonhematologic reaction of grade 3 or higher that has an onset after the start of infusion on an infusion day, responds to symptomatic therapy, and resolves within 6 hours from onset
- Adverse reactions that prevent the infusion from being resumed regardless of the length of the reaction
- Hematologic toxicity, considered related to daratumumab, defined as
 - Thrombocytopenia (platelet count < 20,000 cells/μL)
 - Asymptomatic grade 4 neutropenia for more than 3 days
 - Neutropenic fever (defined as grade 3 or 4 neutropenia and temperature > 38.5°C) for more than 3 days

• Inability to receive the Day 1 infusion of Cycle 2 because of any toxicity related to daratumumab

If noncompliance with protocol-defined requirements results in toxicities of Grade 3 or higher, these toxicities should not qualify as DLTs.

Data from the Study GEN501 have shown the presence of free hemoglobin during daratumumab infusions without any clinical impact. Because this study includes escalating doses of daratumumab and combination therapy, the sponsor has specified that hemolysis greater than Grade 3 will be considered a DLT.

Neutropenic fever (defined as Grade 3 or 4 neutropenia and temperature >38.5°C) for more than 3 days has been specified by the sponsor as a DLT because, if the subject has been treated with G-CSF and the neutropenia has not normalized within 3 days, the bone marrow suppression is severe and clinically important.

Transfusion of platelets should be initiated at a platelet count of <20,000 cells/ μ L to prevent life-threatening thrombocytopenia (<10,000 cells/ μ L).

Subjects who experience a DLT but have demonstrated a response to study drug therapy may remain in the study at the discretion of the investigator at 1 dose level below that at which the DLT occurred.

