For Phase 1 and Phase 2, dexamethasone will be administered at a total dose of 40 mg/week (except for the first week of daratumumab dosing; see below). On the day of the predose infusion of daratumumab (Cycle 1 Visit 1), dexamethasone will be administered at a dose of 20 mg IV before the infusion; no dose will be administered after the infusion. During daratumumab infusion weeks, dexamethasone will be administered on the day of daratumumab infusion as 20 mg IV before the infusion and 20 mg PO the day after the infusion. An equivalent dose may be given in accordance with local standards (Attachment 4). During weeks when no daratumumab infusion is planned, dexamethasone will be administered at a dose of 40 mg/week PO. For both Phase 1 and Phase 2, after the completion of Cycle 6, the administration of dexamethasone may be adjusted at the discretion of the investigator; however, dexamethasone should always be administered at a dose of 20 mg IV on daratumumab infusion days. Dexamethasone will be administered until the subject experiences disease progression or unacceptable toxicity, whichever comes first.

At Cycle 1 Visit 2 (the first full-dose infusion of daratumumab), the subject may either remain hospitalized overnight and be released on the following day or may receive outpatient IV administration at the investigator's discretion. This hospitalization should not be reported as an SAE. Hospitalization is not required for the predose infusion (Cycle 1 Visit 1) because no infusion-related SAEs have been observed during or after the predose infusion of 23 subjects during the GEN501 study.

All subsequent infusions will be performed as outpatient visits. If the subject has not experienced a significant medical event but is hospitalized overnight only for observation, the hospitalization should not be reported as an SAE.

Adverse events will be monitored closely during treatment. Escalation to a new dose level can only be done after evaluation of the safety profile of the previous dose level by the IDMC. After this evaluation, the IDMC will make a recommendation regarding dose escalation.

If the subject must stop either daratumumab, lenalidomide, or dexamethasone, the subject may continue the other components until progression or commencing a new regimen for the treatment of multiple myeloma. However, subjects will still receive dexamethasone as premedication to daratumumab.

9.1.3.1. Treatment Follow-up as per Amendment 8

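### Section 10.2 withdraws subjects for Grade 3 skin rash but does not name Grade 4, so read literally the worse rash falls under Section 6.2.1.5's restart rule; the 10.2 DLT bullet also contradicts Section 6.5, now only on paper.

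*Protocol*

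**What the plan says.** **Withdrawal (Protocol 10.2).** "A subject will be withdrawn from treatment for any of the following reasons". Thirteen reasons follow. Two matter here: DLT, and Grade 3 skin rash. Neither bullet carries an exception, an attribution condition or a reference to Section 6. Grade 4 rash is not named.

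**Lenalidomide dose adjustment (Protocol 6.2.1.5).** This subsection applies to Grade 3 or 4 toxicities, other than those handled just before it, that the investigator attributes to lenalidomide and to no other drug. In that case "treatment with lenalidomide should be interrupted and restarted at the next lower dose level once the toxicity has resolved to Grade 2 or less". It adds: "Treatment with daratumumab and dexamethasone may continue". The preceding subsections (6.2.1.1 to 6.2.1.4) deal with DVT/PE, thrombocytopenia, neutropenia and renal impairment, so rash is among the other toxicities.

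**DLT (Protocol 6.5).** DLTs are defined within the first 28-day cycle. A subject with a DLT who has responded "may remain in the study at the discretion of the investigator at 1 dose level below that at which the DLT occurred".

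**General discretion (Protocol 10.1).** Study treatment should be discontinued when the investigator judges for safety reasons that this is best for the subject.

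**The concern.** A Grade 3 rash attributed solely to lenalidomide meets two rules. One ends treatment; the other resumes the suspected drug at a lower dose. A site cannot follow both, and the choice between stopping and re-exposure is a safety instruction.

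The Grade 4 case is worse. The only rule whose wording reaches a Grade 4 rash directly is the one that restarts the drug. On the page, the protocol is stricter for the less severe event.

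Inconsistent handling would also be hard to see now. Section 12.6.1 limits collection to SAEs from Amendment 7, Section 11.13 ends IDMC safety review after the primary analysis, and Section 17.8 describes on-site visits at intervals of at least 24 weeks.

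**Working it through.** No arithmetic applies. The check sets the rules side by side for each type of event.

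| Event | Section 10.2 | Section 6 | Result |
|---|---|---|---|
| Grade 3 rash, lenalidomide alone | Withdraw | 6.2.1.5: interrupt, restart one level lower | Two opposite instructions |
| Grade 4 rash, lenalidomide alone | Not named; only the investigator-decision and other bullets could apply | 6.2.1.5: interrupt, restart one level lower | Only the restart rule covers it by its terms |
| Grade 3 rash, any other attribution | Withdraw | 6.2.1.5 does not apply | No conflict with 6.2.1.5 |
| DLT in a responder | Withdraw | 6.5: may continue one dose level lower | Direct contradiction |

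**Step 1: Grade 3 rash.** Section 10.2 names the event and uses mandatory wording. Section 6.2.1.5 is general and uses advisory wording. The Amendment 2 entry in the protocol's amendment list shows that the mandatory wording was chosen deliberately: "This amendment corrects that statement to clarify that subjects will be withdrawn from treatment for any of the reasons listed". The sensible reading is that Section 10.2 prevails. Nothing found in the text reviewed says so, however, and neither section refers to the other. Section 6.4 shows that the protocol can write a yielding clause when it wants one: "Nonhematologic toxicity of Grade 3 or higher must have recovered to baseline or Grade 1 or less unless otherwise specified". Section 6.2.1.5 has none.

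**Step 2: Grade 4 rash.** Precedence for Section 10.2 does not help, because its bullet stops at Grade 3. Section 6.2.1.5 expressly includes Grade 4. What remains against a restart is investigator judgement under Section 10.1 or the two open bullets of Section 10.2.

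**Step 3: DLT.** In Section 6.5, remaining in the study cannot mean follow-up without drug, because the clause sets the dose level. The two rules therefore give the same responder opposite instructions.

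**Step 4: timing.** The DLT window is the first 28 days. Section 9.2 says that by Amendment 8 every subject had received at least 24 months of study drug or had discontinued, so nobody can still have a DLT. The rash rules are different: Table 4 and Attachment 9 keep lenalidomide dosing in place, so a lenalidomide rash remains possible.

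**The case against.** The strongest reply is that this is an ordinary overlap of a general and a specific rule. A withdrawn subject has no study lenalidomide to restart, and a dose-adjustment section need not repeat every exit criterion. For Grade 3 rash most of that stands, and it is why the point is minor. It does not answer the Grade 4 gap. Section 10.1 narrows that gap, since an investigator who thinks stopping is right may stop, but it replaces a rule with discretion exactly where the event is more severe.

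Two further limits are fair. Sections 6.2.1 and 12.6.3 refer sites to the lenalidomide label, which is not among the documents and may settle the matter. The part of Attachment 9 after its Treatment Period heading was also not available, so the absence of a precedence rule for ongoing subjects cannot be stated without qualification.

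A reader might infer more than the documents support:

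- *That DLT responders were handled inconsistently.* No document shows that such a subject existed.
- *That tumor lysis syndrome is a second live conflict.* It is listed in Section 10.2, but an overlap would need a Grade 3 or 4 event attributed to lenalidomide alone. The documents nowhere make that attribution; Section 8.1 handles the syndrome by monitoring and prophylaxis.
- *That the dose difference between the two rules measures the impact.* It only restates the dose table. The documents give neither a rash rate nor the number of subjects still treated.
- *That Section 10.2 may mean stopping one drug only.* Section 9.1.3 does say "If the subject must stop either daratumumab, lenalidomide, or dexamethasone, the subject may continue the other components until progression or commencing a new regimen". But the Section 10.2 list, with pregnancy, progression and new myeloma therapy, reads more naturally as withdrawal from the whole regimen.

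**Conclusion.** The wording is wrong in two places, and the severity is minor. The live defect is the rash bullet: it overlaps with Section 6.2.1.5 at Grade 3, where Section 10.2 probably prevails, and leaves Grade 4 to the restart rule unless the investigator intervenes. It arises only when the rash is attributed to lenalidomide alone. The DLT bullet is a plain contradiction of Section 6.5 but can affect no current subject.

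Of the 13 reasons in Section 10.2, one has a live defect and one a historical one. No frequency can be given. A reader might expect an effect on the disposition summaries in SAP 4.2 or the adverse event tables; the documents do not support that. The SAP serves the primary analysis, which Amendment 7 treats as achieved. Sample size, power, planned analyses and efficacy conclusions are untouched.

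The conclusion assumes that neither the lenalidomide label nor the unseen part of Attachment 9 settles the question.

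**What to change.** 1. In Section 10.2, change the rash bullet to *Grade 3 or higher skin rash*.
2. In Section 6.2.1.5, add *except events requiring withdrawal under Section 10.2*.
3. If the text is being amended anyway, change the DLT bullet to *DLT, except as permitted in Section 6.5*.

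The first two edits close the Grade 4 gap and settle precedence. The third only makes the record consistent. No procedures, data or analyses are added. Because a safety instruction changes, the edit is not purely administrative and needs IEC/IRB approval before use (Sections 16.2.2 and 17.1).
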